### **9.2.3.2. IDMC analyses**

Independent review will be provided by an IDMC to ensure external objective medical and/or statistical review of efficacy and safety in order to protect the ethical interests and well-being of subjects and to protect the scientific validity of this study. An ad-hoc review of data by the IDMC will be triggered whenever the number of confirmed virologic failures in the CAB LA + RPV LA Q8W arm exceeds thresholds pre-specified in the IDMC charter. Further, an interim futility analysis will be performed for the IDMC to evaluate the efficacy and safety of CAB LA + RPV LA Q8W arm when approximately 50% of subjects have completed their visit at Week 24; the sponsor will remain blinded to this analysis. Any additional Week 24 analyses will also be shared with the IDMC. Full details of the methods, timing, decision criteria and operating characteristics will be pre-specified in the IDMC Charter.

Since the statistical stopping guidelines will not result in early stopping due to positive efficacy findings for the Q8W regimen, these planned analyses will not inflate the type I error rate for the primary treatment comparison at Week 48.

## **9.3. Key Elements of Analysis Plan**

### **9.3.1. Primary Analyses**

For the primary efficacy analysis, virologic outcome for each participant in the Intent-to-Treat Exposed population will be calculated according to the FDA's Snapshot algorithm. The primary analysis at Week 48 will take place after the last participant has had their Week 48 viral load assessed, including a retest if required.

As defined by the Snapshot algorithm, HIV-RNA  $\geq 50$  copies/mL is determined by the last available HIV-1 RNA measurement while the participant is on treatment within the

analysis visit window of interest. In addition, participants without evaluable HIV-RNA data for the visit of interest and who discontinue from the maintenance phase for reasons not related to adverse event with HIV-1 RNA result at the time of discontinuation  $\geq 50$  copies/mL or who change study treatment not permitted per protocol before the analysis window are classified as having HIV-RNA  $\geq 50$  copies/mL.

For the primary efficacy analysis, the adjusted difference between the randomized arms for the proportion of participants with HIV-1 RNA  $\geq 50$  c/mL at Week 48 (according to the FDA snapshot algorithm) and its confidence interval will be calculated according to a stratified analysis with Cochran-Mantel Haenszel (CMH) weights. This analysis will adjust for the randomization strata (rederived for analysis to correct for stratification errors) according to prior exposure to CAB + RPV (0 weeks, 1-24 weeks, >24 weeks).

The CMH estimate of the common difference in rates across strata will be calculated as the weighted average of the strata-specific estimates of the difference in proportion between the two arms as follows:

- If  $n_k$  is the number of Q8W treated participants,  $m_k$  is the number of Q4W arm treated participants, and  $N_k = n_k + m_k$  is the total number of participants in the  $k$ th stratum, then the CMH estimate is given by

$$\hat{d}_{cmh} = \frac{\sum W_k \hat{d}_k}{\sum W_k}$$

where

$$W_k = \frac{n_k m_k}{N_k}$$

are CMH weights and  $\hat{d}_k$  are estimates of the differences in proportions between the two treatment arms,  $f_{Q8W} - f_{Q4W}$ , for the  $k$ th stratum.

The corresponding two-sided 95% CI will be calculated as:

$$\hat{d}_{cmh} \pm 1.96 \times \sqrt{\widehat{\text{var}}(\hat{d}_{cmh})}$$

using the variance estimator given by [Sato, 1989], which is consistent in both sparse data and large strata. The formula for computing the Sato variance estimate will be provided in the RAP. Non-inferiority will be declared if the upper bound of the two-sided 95% confidence interval for the difference (Q8W – Q4W) is less than 4%.

The weighted least squares chi-squared statistic [Fleiss, 1981] will be used to assess evidence of treatment difference heterogeneity across strata. strata, Following Lui and Kelly [Lui, 2000], 0.50 will be added to each cell in any strata for which the stratum-

specific rate estimates of either  $f_{Q8W}$  or  $f_{Q4W}$  are zero or one. Any heterogeneity found to be statistically significant will be explored. Stratum-specific analyses will also be provided. Investigation of heterogeneity will be confined to the primary endpoint. Tests of homogeneity will be assessed at the one-sided 10% level of significance. Full details will be contained in the RAP.

On-treatment data collected from extra visits within a window will be included in the derivation of the Snapshot response/failure but summary tables using observed case (OC) datasets will only use the data captured closest to the target visit date. Detailed explanations of the derivation of visit windows will be included in the RAP. Any changes to the original analysis plan in the protocol will be described in the RAP and/or clinical study report (CSR).

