#### **7.5. Pharmacokinetics**

Plasma samples for determination of CAB and RPV concentrations will be collected throughout the Maintenance and Extension Phases of the study. Additional samples will be collected for storage during the LTFU Phase (blood and plasma). Samples (blood and plasma) for determination of RPV concentrations will be protected from light at all times, from sampling collection through analysis.

Pregnant participants will have additional PK samples collected during the duration of the pregnancy. See [Appendix 11](#) for details.

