### **7.8.2. Value Evidence and Outcomes Endpoints (Exploratory)**

- The “Reason for Switch” question will be administered at Day 1 (Baseline) for patients randomized from oral SOC, to assess the reasons for willingness to switch ART.
- The “Reason for Switch” question will be administered at Day 1(Baseline) for patients randomized from CAB LA + RPV LA every 4 weeks in ATLAS, to assess the reasons for willingness to continue long-acting ART.
- A preference questionnaire will be administered to participants receiving oral bridging during the Maintenance and/or Extension Phases in order to explore preference for CAB + RPV LA Q4W or Q8W compared to daily oral HIV medication at W152 or upon WD visit if occurred at or before Week 152.

**7.8.3. Guidance for administering the different versions of HIVTSQc, Preference and Reason for Switch Questionnaires in ATLAS-2M**

*For the questionnaires not included below, HIVTSQs, HAT-QoL, ACCEPT and PIN, there only exists one version of each PRO that will be administered to all patients.*

Questionnaire	Version	Week visit in ATLAS-2M	Treatment Arm in ATLAS-2M	Treatment before entering ATLAS-2M	Patients in Extension phase in ATLAS
HIVTSQc	Q4W ATLAS to Q4W ATLAS-2M	Week 48 / Withdrawal	Currently on Q4W	Randomized at Day 1 in Q4W arm in ATLAS	Even if patients remained in extension phase in ATLAS consider only the initial arm they were randomized in Day 1 in ATLAS
	Q4W ATLAS to Q8W ATLAS-2M	Week 48 / Withdrawal	Currently on Q8W	Randomized at Day 1 in Q4W arm in ATLAS	
	SOC to Q4W or Q8W ATLAS-2M	Week 48 / Withdrawal	Currently on Q4W or Q8W	Any SOC treatment:  Randomized at Day 1 in SOC in ATLAS or coming outside of ATLAS	
Preference	Injection to Injection treatment	Week 48 / Withdrawal	Currently on Q8W	Randomized at Day1 in Q4W arm in ATLAS	Even if patients remained in extension phase in ATLAS consider only the initial arm they were randomized in Day 1 in ATLAS
	Oral to Injection treatment	Week 48 / Withdrawal	Currently on Q4W or Q8W	Any SOC treatment:  Randomized at Day 1 in SOC in ATLAS or coming outside of ATLAS  Continuing	

Questionnaire	Version	Week visit in ATLAS-2M	Treatment Arm in ATLAS-2M	Treatment before entering ATLAS-2M	Patients in Extension phase in ATLAS
				Q4W from ATLAS	
	Reason for Oral Bridging and Preference questionnaire	Week 152 / Withdrawal	Currently on Q4W or Q8W	SOC and Q4W from ATLAS	Not applicable.

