### **9.3.2. Secondary Analyses**

#### **9.3.2.1. Key Secondary Efficacy Analysis**

A key secondary analysis will evaluate the proportion of participants with HIV-1 RNA  $<50$  c/mL (according to the FDA's Snapshot algorithm) at Week 48 for the ITT-E population. Participants with last available HIV-1 RNA measurement less than 50 copies/mL while the participant is on treatment within the analysis visit window of interest are classified as responders; participants without evaluable HIV-RNA data for the visit of interest or who change treatment not permitted per protocol before the analysis window are considered non-responders. Full details on the Snapshot algorithm for computation of the proportion with HIV-1 RNA  $<50$  copies/mL will be contained in the RAP. The adjusted difference between the randomized arms for the proportions (Q8W – Q4W) and its confidence interval will be calculated according to a stratified analysis with Cochran-Mantel Haenszel (CMH) weights, as described for primary endpoint (Section 9.3.1).

A non-inferiority margin of -10% will be used for this secondary comparison, where if the lower limit of the 95% confidence interval (CI) of the difference between the rates (Q8W – Q4W) is greater than -10%, non-inferiority will be demonstrated.

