#### **9.3.2.2. Other Secondary Endpoint Analyses**

The primary analysis (Section 9.3.1) and key secondary efficacy analysis (Section 9.3.2.1) will be repeated at Week 96 and Week 152 with the only difference being a change in time point from Week 48 to Week 96 or Week 152 for determining the snapshot outcomes.

For the Week 24 planned analyses, the adjusted treatment difference in proportion of participants with plasma HIV-1 RNA  $\geq 50$  c/mL (FDA Snapshot algorithm, with 95% confidence interval) at Week 24 will be calculated using the methodology described in Section 9.3.1, but no formal test of non-inferiority will be performed at this early timepoint.

Proportion of participants with plasma HIV-1 RNA  $\geq 50$  c/mL and HIV-1 RNA  $< 50$  c/mL (FDA Snapshot algorithm) at Week 24, Week 48, Week 96, and Week 152 respectively, will be summarized using the Snapshot algorithm for the ITT-E population. Proportion of participants with confirmed virologic failures will also be summarized over time.

Absolute values and change from Baseline in CD4+ lymphocyte count will be summarized over time including Week 48, Week 96, and Week 152.

The proportion of participants with HIV-1 RNA  $\geq 50$  c/mL based on the snapshot algorithm, will be summarized at Week 24, Week 48, Week 96, and Week 152 by duration of prior CAB + RPV exposure (0 weeks, 1-24 weeks,  $> 24$  weeks),

The proportion of participants with HIV-1 RNA  $< 50$  c/mL based on snapshot algorithm, will be summarized at Week 48, Week 96, and Week 152 by duration of prior CAB + RPV exposure (0 weeks, 1-24 weeks,  $> 24$  weeks).

An observed case dataset, with no imputation for missing data, will be the primary dataset used for analysis of safety endpoints.

The proportion of participants reporting AEs will be tabulated for each treatment group. The following summaries of AEs will be provided:

- Incidence and severity of all AEs
- Incidence and severity of treatment related AEs
- Incidence and severity of AEs leading to withdrawal
- Incidence of SAEs

Changes from baseline in laboratory will be summarized by visit and treatment group including Week 48, Week 96, and Week 152. In addition, the number and percentage of participants with graded laboratory toxicities (based on DAIDS categories) will be summarized by treatment group.

Further details for secondary efficacy, safety, and exploratory endpoint analyses will be included in the RAP.

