Section 1.4.3 and Section 4.2.3 Extension Phase	Text in bold was added:  Participants who successfully complete 96 Weeks of CAB LA + RPV LA treatment in the Maintenance Phase will continue to have access to their randomized treatment Q4W or Q8W CAB LA + RPV LA in the Extension Phase through Week 152 and until study treatment is either locally approved and commercially available...	Extends participant access to randomized study treatment through Week 152 at minimum.
Section 1.4.4 Long-Term Follow-Up Phase	Text in bold was added:  Investigators must discuss the choice of the follow-up HAART regimen with the Medical Monitor prior to initiating the new regimen with the participant. HAART therapy should be initiated within 4 weeks ( +7 days ) after the last Q4W injection, or within 8 weeks ( +7 days ) after the last Q8W injection	Clarification is added to the allowed window for initiation of HAART therapy following the last CAB LA + RPV LA IM injections received.
Section 5.5 Withdrawal/Stopping Criteria	Text in bold was added:  If withdrawal coincides with the active planned Week 52, Week 100, or Week 156 (Q4W arm) visits, HIV-1 RNA will only be assessed if the last HIV-RNA measurement from Week 48, Week 96, or Week 152 was $\geq 50$ copies per mL (i.e. retest for viral load blip). This will ensure that only the Week 48, Week 96, and Week 152 viral load assessments or required retest will be counted towards the primary and secondary efficacy endpoint windows.	Maintains consistency with HIV-1 RNA analysis and retest strategy
5.5.5.1 HIV-1 RNA Blips	Text in bold was added:  Participants who have a HIV-1 RNA $\geq 50$ c/mL and $< 200$ c/mL at the key analysis timepoints (Week 48, Week 96, and Week 152 ) must return to	Incorporates similar HIV-1 RNA retesting strategy for Week 152 visit that was utilized for prior Week 48 and 96

Section # and Name	Description of Change	Brief Rationale
	the clinic as soon as possible (but no later than 4 weeks after the date of the Week 48, 96, or 152 visit, respectively	timepoints.
6.8.1 Oral Bridging	The following text was added: Participants who withdraw during an oral treatment period must be initiated on HAART therapy within 24 hours after the last oral treatment with CAB + RPV.	Clarification regarding guidance for initiation of HAART therapy for participants withdrawing during oral treatment.

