Section # and Name	Description of Change	Brief Rationale
Synopsis Section 1.4.2, and Section 4.2.2, Maintenance Phase (Day1 up to Week 100), CAB LA + RPV LA Dosing Regimens in ATLAS-2M	Clarified for Q8W cohort transitioning from Oral Standard of Care (SOC) that CAB LA + RPV LA is administered at Week 4b, Week 8, & Q8W thereafter. (Week 8 was added)	Week 8 dosing for this group was inadvertently omitted in Amendment #1 of the prior protocol within these sections and is now updated for consistency with the intended dosing administration in other sections of the protocol.
Synopsis Section 1.2, Section 3 Objectives and Endpoints;	Select secondary efficacy and safety endpoints have been updated to include Week 24 endpoints.	Adds the additional analysis of data through Week 24 with the intent of expediting the submission of study results to Health Authorities
Synopsis Section 1.2, Section 3 Objectives and Endpoints; Section 7.8, Value Evidence and Outcomes; Section 7.8.1, Value Evidence and Outcomes Endpoints (Secondary); Section 9.3.7, Health Outcomes Analyses.	Assessment of the preference for CAB LA + RPV LA every 8 weeks or CAB LA + RPV LA every 4 weeks LA compared to oral antiretroviral (ARV) and the preference for CAB LA+ RPV LA every 8 weeks compared to CAB LA + RPV LA every 4 weeks is changed from an exploratory objective to a secondary objective of ATLAS-2M. The description of the Preference questionnaire is updated to reflect the revised questionnaire. The Preference questionnaire will be captured at Week 48 or Withdrawal if prior to Week 48.	The version of the Preference questionnaire has been updated and re-purposed as a secondary objective for the ATLAS-2M trial.
Section 4.2.4, LTFU Phase-IM Regimen Only	Window for initiating HAART therapy during the LTFU Phase has been added:  HAART therapy should be initiated within 4 weeks ( ± 7 days ) after the last Q4W injection, or within 8 weeks ( ± 7 days ) after the last Q8W injection.	Allowable window for the initiation of HAART therapy ensures timely start of HAART during the LTFU Phase to approximate exposure coverage for CAB LA + RPV LA.

Section # and Name	Description of Change	Brief Rationale

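### The discontinuation clause for Snapshot HIV-RNA ≥50 c/mL names only the Maintenance Phase but is carried unchanged to Week 152, which lies in the Extension Phase

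*Protocol*

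**What the plan says.** Section 9.3.1 (Primary Analyses) sets out when a participant is classed as Snapshot HIV-RNA ≥50 c/mL. The main route is the last on-treatment RNA in the analysis window. For participants with no evaluable RNA at the visit, two further routes are given:

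- those "who discontinue from the maintenance phase for reasons not related to adverse event with HIV-1 RNA result at the time of discontinuation" at or above 50 c/mL;
- those "who change study treatment not permitted per protocol before the analysis window".

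The first of these names a phase and the second does not.

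Section 9.3.2.2 (Other Secondary Endpoint Analyses) says that the primary and key secondary efficacy analyses "will be repeated at Week 96 and Week 152 with the only difference being a change in time point" used to determine the Snapshot outcomes.

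The protocol treats Maintenance and Extension as separate phases. Section 7.5 says that PK samples "will be collected throughout the Maintenance and Extension Phases of the study", and Section 7.8.2 refers to oral bridging "during the Maintenance and/or Extension Phases". The amendment history in Appendix 14 helps to date them. The Amendment 2 table cites a section headed "Maintenance Phase (Day1 up to Week 100". The Amendment 4 table describes the Extension Phase in these terms: "Participants who successfully complete 96 Weeks of CAB LA + RPV LA treatment in the Maintenance Phase will continue to have access" to randomized treatment, now through Week 152.

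The responder rule in Section 9.3.2.1 has no phase limit: "participants without evaluable HIV-RNA data for the visit of interest or who change treatment not permitted per protocol" before the window are non-responders.

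**The concern.** The phase limit does no harm at Week 48 or Week 96, because anyone who stops before those windows stops during Maintenance. At Week 152 it matters. A participant withdrawn at Week 120, say, for a non-AE reason with RNA ≥50 c/mL leaves the Extension Phase and has no RNA in the Week 152 window. That participant does not meet the discontinuation clause.

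The treatment-change clause does not clearly capture the case either. Participants who stop after long-acting dosing are directed to start HAART and enter long-term follow-up (for example Sections 7.4.5.5, 7.4.5.6 and 7.4.5.13). A switch that the protocol itself directs is not plainly one that it does not permit.

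The Week 152 analysis looks at durability. Withdrawal with RNA ≥50 c/mL is one way in which a late failure can leave without Week 152 data. If such cases drop out of the ≥50 c/mL count, the Week 152 failure rate is understated. The Q8W minus Q4W difference then shifts according to which arm lost more of them.

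**Working it through.** **The text**

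1. Section 9.3.1: the discontinuation route to ≥50 c/mL requires leaving the Maintenance Phase.
2. Section 9.3.2.2: at Week 152 only the time point changes, so nothing in the current text widens that route.
3. Week 152 falls in the Extension Phase. The Amendment 4 table places the Extension after 96 weeks of Maintenance. In the current text, Section 11.13.4.1.1 requires at least 152 weeks of treatment for the thigh sub-study, and Section 11.13.4.5 returns completers to the Extension Phase where marketed product is not yet available.
4. A likely origin: the Amendment 4 table lists Sections 9.2.3, 9.3.2.2 and 9.3.9 among the statistical sections edited to add Week 152. Section 9.3.1 is not listed.

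Outcome at Week 152 under the written rules, for a participant with no RNA in the window and no non-permitted treatment change:

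| Participant | ≥50 c/mL (9.3.1) | <50 c/mL (9.3.2.1) |
|---|---|---|
| Non-AE, RNA ≥50, left Maintenance | Yes | Non-responder |
| Non-AE, RNA ≥50, left Extension | Not classified | Non-responder |
| Left for an AE, either phase | Not by this clause | Non-responder |

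The first two rows differ only in the phase.

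**The protocol's own figures**

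Inputs from Section 9.1: 510 per arm, true rates 3% (Q8W) and 2% (Q4W), margin 4%, one-sided 2.5%, unpooled Z.

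- SE = √(0.03×0.97/510 + 0.02×0.98/510) = 0.00977.
- Power = Φ((0.04 − 0.01)/0.00977 − 1.96) = Φ(1.11) = 86.7%. The protocol states at least 85%, so this reproduces.
- With Q4W at 2%, the largest observed difference whose upper bound stays below 4% is 1.92 points, as stated.

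These are Week 48 figures and the clause does not touch them.

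**Size at Week 152**

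The documents give no count of Extension Phase leavers with RNA ≥50 c/mL, so every count below is an assumption. Each omitted participant lowers an arm's rate by 1/510 = 0.20 points. The upper bound is d + 1.96 × √(p₈(1−p₈)/510 + p₄(1−p₄)/510), without stratification.

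| Assumed true failures, Q8W v Q4W | Omitted | Counted | Difference (points) | Upper 95% bound |
|---|---|---|---|---|
| 22 v 10 | none | 22 v 10 | 2.35 | 4.49% |
| 22 v 10 | 2 in Q8W | 20 v 10 | 1.96 | 4.03% |
| 22 v 10 | 4 in Q8W | 18 v 10 | 1.57 | 3.57% |
| 22 v 10 | 6 in Q8W | 16 v 10 | 1.18 | 3.11% |
| 20 v 14 | none | 20 v 14 | 1.18 | 3.38% |
| 20 v 14 | 4 in Q4W | 20 v 10 | 1.96 | 4.03% |
| 22 v 12 | none | 22 v 12 | 1.96 | 4.16% |
| 22 v 12 | 2 in each | 20 v 10 | 1.96 | 4.03% |

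For the first row: 12/510 = 0.0235, SE = 0.01089, and 0.0235 + 1.96×0.01089 = 0.0449.

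Omissions in Q8W lower the bound and omissions in Q4W raise it. Equal omissions leave the difference unchanged, understate both rates and slightly narrow the interval. The starting counts were chosen near the margin to show the mechanism and predict nothing.

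**The case against.** The strongest reply is that the FDA Snapshot algorithm governs. Section 9.3.1 names it, presents the sentence as its definition, and sits in the Week 48 section, where every earlier discontinuation is from Maintenance. Section 9.3.2.2 speaks of determining the Snapshot outcomes at the new time point, so a sensible programmer would adapt the phase label too. The analysis plan, not shown here, may already do so. This lowers the practical risk and means the text does not show how the data will be programmed. It does not cure the text: the protocol writes out the rule as its own statement of the algorithm, and that statement is wrong for Week 152.

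The phase dates rest partly on the amendment history, and the sections defining the phases are in the part of the protocol not shown. Amendment 4 also edited the Maintenance Phase sections to add Week 152. Even so, the Amendment 4 description of the Extension Phase and the sub-study text both place Week 152 in the Extension.

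Three stronger readings are tempting, and the documents do not support them:

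- **These participants are lost as virologic failures.** They are not. Section 9.3.2.2 summarises confirmed virologic failures over time, Section 9.3.6 summarises their resistance, and Section 9.3.2.1 counts all of these leavers as non-responders.
- **The rule biases toward non-inferiority.** It does so only if the omitted cases are mainly in Q8W.
- **The two Snapshot endpoints should be mirror images.** They are not complements by design, as AE leavers already show. The narrower point is that the same kind of non-AE leaver is classified differently according to phase.

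**Conclusion.** The point holds as a misstated rule with limited reach. Read as written, non-AE Extension Phase leavers with RNA ≥50 c/mL and no Week 152 window data are not classified as Snapshot ≥50 c/mL at Week 152 through the discontinuation clause. The effect is about 0.2 points per omitted participant per arm, with the direction set by the arm in which the omissions fall. How many there would be is unknown.

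The conclusion rests on two readings: that Week 152 is in the Extension Phase, and that a protocol-directed switch to HAART after withdrawal is not a non-permitted treatment change. Extension leavers who do make a non-permitted change, or who have an on-treatment value ≥50 c/mL in the window, are still counted.

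Week 48 is the primary analysis, and the sequence of tests in Section 9.2.2.2 is at Week 48. Week 152 is a secondary repeat outside that sequence. No Week 48 or Week 96 result, power figure or sample size changes.

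**What to change.** In Section 9.3.1, replace the maintenance-phase limit with wording such as *discontinue study treatment (Maintenance Phase, or Extension Phase for Week 152)*. Alternatively, state in Section 9.3.2.2 that the clause covers Extension Phase discontinuations at Week 152, consistent with the named Snapshot algorithm. Check that the analysis plan says the same.

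The cost is one sentence and no new data. The small downside is that Week 152 failure rates may be slightly higher than under the present wording.

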### 9.1. Sample Size Considerations

This study will randomize approximately 510 participants per arm. Assuming the true proportion with HIV-1 RNA  $\geq 50$  c/mL is 3% for the Q8W arm and 2% for the Q4W arm, a non-inferiority margin of 4%, and a 2.5% one-sided significance level, this sample size would provide at least 85% power to show non-inferiority at Week 48 (using unpooled Z test statistic). With this sample size, 90% power would be achieved assuming a 1% treatment difference and true proportions with HIV-1 RNA  $\geq 50$  c/mL of 2.63% for the Q8W arm and 1.63% for the Q4W arm.

With 510 subjects per arm and assuming an observed proportion HIV-RNA  $\geq 50$  c/mL is 2% for Q4W, the largest observed treatment difference to achieve non-inferiority with respect to a 4% margin is 1.92 percentage points. This equates approximately to observing an excess of 10 subjects on the Q8W arm (10 subjects on Q4W vs. 20 subjects on Q8W).

This sample size of 510 participants per arm will also provide at least 90% power (using unpooled Z test statistic) to show non-inferiority in the proportion of participants with plasma HIV-1 RNA  $< 50$  c/mL (per FDA's snapshot algorithm) at Week 48 over a range of true response rates, on the basis of a -10% non-inferiority margin and 2.5% one-sided significance level (see [Figure 15](#)). For example, assuming true response rate for the Q8W arm and Q4W arm are both 92%, the power is  $\geq 99\%$  to show non-inferiority for this key secondary endpoint.

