### 9.1.4. Sample Size Sensitivity

Figure 15a (left panel) shows the sensitivity of the power curve for the primary comparison to different assumed 'true' proportions with HIV-RNA  $\geq 50$  c/mL with 510

randomized participants per arm based on calculations using an unpooled Z test statistic and asymptotic approximation. For example, if the true rate for Q8W is 1.5 percentage points higher than Q4W (green line), then the study would still have over 80% power to meet its primary objective if the Q4W rate is less than 1.3%.

Figure 15b (right panel) shows the impact on power to changes in the sample size assuming a 2% true-rate for Q4W. Power remains at least 80% for sample sizes as low as 425 per arm if the true Q8W rate is at most 1-percentage point inferior to Q4W.

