### **9.2.2. Treatment Comparisons**

#### **9.2.2.1. Primary Comparison of Interest**

The primary analysis will be based on the ITT-E population. The primary comparison will be made at a one-sided 2.5% level of significance. Treatment with Q8W will be declared non-inferior to Q4W if the upper end of a two-sided 95% confidence interval for the difference between the two groups (Q8W – Q4W) in the proportion of participants with HIV-RNA  $\geq 50$  c/mL at Week 48 (defined by the US FDA snapshot algorithm) lies below 4%.

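### The primary rule (CMH difference plus 1.96 Sato standard errors, below 4%) has a true one-sided error of about 3.2% to 3.7% at Q4W failure rates of 2% to 1%, not the declared 2.5%

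*Protocol*

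**What the plan says.** Section 9.3.1 fixes the interval completely apart from the variance formula, which it leaves to the RAP. It specifies a CMH-weighted risk difference over three strata of prior CAB + RPV exposure, a multiplier of 1.96, and Sato's variance, "which is consistent in both sparse data and large strata". Non-inferiority is declared if the upper limit is below 4%. Section 9.2.2.1 gives the level: "The primary comparison will be made at a one-sided 2.5% level of significance".

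Section 9.1 sets the size: "This study will randomize approximately 510 participants per arm". It assumes that the proportion with HIV-1 RNA of at least 50 "c/mL is 3% for the Q8W arm and 2% for the Q4W arm", with "a non-inferiority margin of 4%, and a 2.5% one-sided significance level", and concludes that there is "at least 85% power to show non-inferiority at Week 48". It adds 90% power at 2.63% versus 1.63%. Section 9.1.4 gives the basis of its power curves: "randomized participants per arm based on calculations using an unpooled Z test statistic and asymptotic approximation".

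The only statement on type I error in the statistical section concerns the interim looks (9.2.3.2). The actual error rate of the primary rule at low event counts is not discussed.

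**The concern.** The interval has Wald form: its standard error comes from the observed rates, not from rates compatible with a 4-point difference. In this setting the estimate and its standard error move together. A sample with unusually few Q8W failures has both a small difference and a small standard error, so its upper limit falls below 4% too often. Consistency of the variance estimator is a large-sample property and does not repair the tail when only some 10 to 30 failures are expected per arm at the margin.

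The error goes one way, towards declaring non-inferiority. The test also gates the key secondary comparisons (9.2.2.2), and 9.3.2.2 repeats the method at Weeks 96 and 152. The excess grows as the Q4W rate falls. Section 9.1.2 itself says that rates may be lower than in the phase 2b study, where Q4W had 1/115 (0.9%) at Week 48.

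**Working it through.** **Inputs.** From 9.1 and 9.3.1: 510 per arm, margin 0.04, multiplier 1.96, planning rates 3%/2% and 2.63%/1.63%, three strata. Stratum sizes are not given, so they were assumed and varied.

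**1. The plan's own figures.** Unpooled-Z power is Φ((0.04 − 0.01)/SE − 1.96).
- 3% v 2%: SE = √(0.03×0.97/510 + 0.02×0.98/510) = 0.00977. Then 0.03/0.00977 = 3.070, and Φ(1.110) = 86.7%. Stated: at least 85%.
- 2.63% v 1.63%: SE = 0.00904, 0.03/0.00904 = 3.320, and Φ(1.360) = 91.3%. Stated: 90%.
- Largest passing difference at Q4W 2%: 0.0192 + 1.96 × √(0.0392×0.9608/510 + 0.02×0.98/510) = 0.0192 + 0.0208 = 0.0400. Stated: 1.92 points.

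All three reproduce.

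**2. The mechanism in one example.** Take 5 Q4W and 16 Q8W failures. The difference is 11/510 = 2.16 points and the observed-rate SE is √(16/510×494/510/510 + 5/510×505/510/510) = 0.00887. The upper limit is 2.16 + 1.96×0.887 = 3.90%, which passes. If the true rates were 1% and 5%, the SE would be √(0.05×0.95/510 + 0.01×0.99/510) = 0.01061, and the same sum gives 2.16 + 2.08 = 4.24%.

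**3. Exact type I error.** Sum Binomial(510, p+0.04) × Binomial(510, p) over all outcomes whose upper limit is below 4%, where p is the Q4W rate. With one stratum, the unpooled Wald and Sato rules agree to four decimals.

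| Q4W rate | Planned rule | Miettinen-Nurminen score |
|---|---|---|
| 2% | 3.19% | 2.37% |
| 1.5% | 3.37% | 2.34% |
| 1% | 3.66% | 2.26% |
| 0.5% | 4.04% | 2.07% |

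Relative to 2.5%, the planned rule is 3.19/2.5 = 1.28 times nominal at 2% and 3.66/2.5 = 1.46 times at 1%.

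**4. Stratification.** The three-stratum CMH/Sato rule was simulated with 1,000,000 trials per setting and per-arm strata of 320/60/130, 255/55/200, 170/170/170 and 400/30/80. Its error is 3.2% at Q4W 2%, 3.6–3.7% at 1% and 4.0–4.1% at 0.5%. With unequal stratum rates or differences and a pooled Q4W rate near 1%, it is 3.6–3.7%. With 425 to 522 per arm and one stratum, the range over Q4W 1–2% is about 3.1–3.8%.

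**5. Exact power.**

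| True rates | Planned rule | Score rule |
|---|---|---|
| 3% v 2% | 85.8% | 81.2% |
| 2.63% v 1.63% | 90.0% | 85.5% |

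The score rule uses less than its 2.5%. If the planned form is kept and the multiplier raised until size is at most 2.5%, about 2.085 is needed at Q4W 2% (power 82.2% at 3% v 2%), or about 2.155 to cover Q4W 1–2% (80.5%).

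**6. Decision boundary.** Largest passing Q8W count, planned v score: 13 v 11 with 0 Q4W failures, 15 v 13 with 3, 16 v 15 with 5, 18 v 17 with 8, 19 v 19 with 10, 21 v 20 with 12. From 4 Q4W failures up to 30, the rules differ by one event or none.

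**The case against.** The strongest defence is that this is a named, cited and pre-specified stratified method, that 2.5% is its nominal asymptotic level, and that the power basis is disclosed. Sample size and analysis match each other, and the unseen RAP may add a score interval as a sensitivity analysis.

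Much of this stands, and it rules out several stronger readings that a reader might infer:
- That the sentence on Sato's variance is false. It is not: it describes the estimator and promises nothing about tail error in finite samples.
- That 85% and 90% are miscalculated. They are correct for the planned unpooled test, exactly as well as asymptotically.
- That the error reaches 4% at the planning rates. At Q4W 1–2% it is 3.2–3.7%. About 4.0–4.1% needs a Q4W rate near 0.4–0.5%, and the 0.9% in Table 11 rests on one event in 115.
- That the whole power gap is the price of correct size. At 3% v 2%, 85.8 − 82.2 = 3.6 points come from holding the level, and 82.2 − 81.2 = 1.0 point from the score method's own conservatism.
- That the trial's conclusion would probably reverse. Only a result one or two events from the boundary could.

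The defence does not remove the main point. Sections 9.2.2.1 and 9.3.1 themselves fix the level, multiplier and decision rule, and that rule exceeds that level at the protocol's own planning rate. A sensitivity analysis in the RAP would not change the size of the primary test.

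**Conclusion.** The point holds, with moderate severity. The primary rule exceeds its declared one-sided 2.5% by about 0.7 points at Q4W 2% and 1.2 points at 1%, always in favour of non-inferiority, and stratification does not cure it. The stated power is right for the planned test but falls to about 80.5–82% at 3% v 2% once the error is held at 2.5%.

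Assumptions: equal arms of 510 with no loss between randomisation and ITT-E, independent binomial counts, and assumed stratum sizes, to which the result is insensitive. The score figures are single-stratum enumerations. A stratified score version should be checked once the actual stratum sizes are known.

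**What to change.** In 9.3.1, take the two-sided 95% interval for the difference from a stratified Miettinen-Nurminen (score) method with the same three strata and CMH weights. Keep the 4% rule, and report the CMH/Sato interval as supportive. Carry the change into the repeats at Weeks 96 and 152. In 9.1, restate power as about 81% at 3% v 2% and about 85% at 2.63% v 1.63% under that interval, and note that a test with size exactly 2.5% at Q4W 2% would have about 82% at 3% v 2%.

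The cost is a text change and standard software. No extra participants are needed, but the stated power drops by 4 to 5 points.

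If Week 48 has already been analysed under the present text (the thigh sub-study section cites observed Week 96 main-study data), the pre-specified result should not be replaced after the fact. Report the score interval beside it and disclose the actual size of the planned rule.
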